### **8.13. Eliciting Adverse Event Information**

The investigator is to report all directly observed AEs and all AEs spontaneously reported by the study subject. In addition, each study subject will be questioned about AEs.

### **8.14. Reporting Requirements**

Each AE is to be assessed to determine if it meets the criteria for SAEs. If an SAE occurs, expedited reporting will follow local and international regulations, as appropriate.

#### **8.14.1. Serious Adverse Event Reporting Requirements**

If an SAE occurs, Pfizer is to be notified within 24 hours of investigator awareness of the event.

In particular, if the SAE is fatal or life-threatening, notification to Pfizer must be made immediately, irrespective of the extent of available AE information. This time frame also applies to additional new information (follow-up) on previously forwarded SAE reports as well as to the initial and follow-up reporting of exposure during pregnancy, exposure via breastfeeding and occupational exposure cases.

In the rare event that the investigator does not become aware of the occurrence of an SAE immediately (eg, if an outpatient study subject initially seeks treatment elsewhere), the investigator is to report the event within 24 hours after learning of it and document the time of his or her first awareness of the AE.

For all SAEs, the investigator is obligated to pursue and provide information to Pfizer in accordance with the time frames for reporting specified above. In addition, an investigator may be requested by Pfizer to obtain specific additional follow-up information in an expedited fashion. This information collected for SAEs is more detailed than that captured on the AE CRF. In general, this will include a description of the AE in sufficient detail to allow for a complete medical assessment of the case and independent determination of possible causality. Information on other possible causes of the event, such as concomitant medications, vaccines, and/or illnesses, must be provided. In the case of a subject death, a summary of available autopsy findings must be submitted as soon as possible to Pfizer or its designated representative.

#### **8.14.2. Nonserious Adverse Event Reporting Requirements**

All AEs will be reported on the AE page(s) of the CRF. It should be noted that the form for collection of SAE information is not the same as the AE CRF. Where the same data are collected, the forms must be completed in a consistent manner. For example, the same AE term should be used on both forms. AEs should be reported using concise medical terminology on the CRFs as well as on the form for collection of SAE information.

#### **8.14.3. Medical Device Reporting Requirements**

All medical device complaints regardless of whether the medical device complaint is associated with an AE will be collected on the applicable pages within the CRF. This includes potential incidents or malfunctions associated with the use of a medical device

product. An incident or malfunction is an event that might have led to death or serious deterioration in health, or if it occurred again might have led to death or serious deterioration in health.

Pfizer is to be notified of all medical device complaints within 24 hours of the investigator's awareness of the event.

Refer to the Pharmacy Manual for procedures for forwarding medical device complaints not associated with an SAE to Pfizer.

#### **8.14.4. Sponsor's Reporting Requirements to Regulatory Authorities**

AE reporting, including suspected unexpected serious adverse reactions, will be carried out in accordance with applicable local regulations.

### **9. DATA ANALYSIS/STATISTICAL METHODS**

Detailed methodology for summary and statistical analyses of the data collected in this study will be documented in a statistical analysis plan (SAP), which will be maintained by the sponsor. This document may modify the plans outlined in the protocol; however, any major modifications of the primary endpoint definition and/or its analysis will also be reflected in a protocol amendment.

#### **9.1. Sample Size Determination**

The primary efficacy endpoint is the change from Baseline to Week 8 in the average daily pain intensity in the index bone metastasis cancer pain site measured by the 11-point Pain Intensity NRS.

From a prior study (A4091003), the assumed within-group standard deviation for the change from Baseline in the Average Pain NRS is 2.0. The targeted mean treatment difference for tanezumab 20 mg SC + opioids versus placebo + opioids is -1.0. A Group Sequential Design with a single interim analysis will be used for the assessment of futility and efficacy of the primary efficacy parameter (refer to [Section 9.6](#) for details).

The interim analysis will be performed when at least 50% (36 from each treatment group) of subjects have completed or discontinued prior to Week 8. Based on current enrollment, it is expected that the interim analysis will include approximately 36 to 45 subjects per treatment group.

Based on data from the previous cancer pain study (A4091003), and not accounting for the assessment of futility and efficacy at the interim analysis, a sample size of approximately 72 subjects per treatment group is required to achieve 85% power to demonstrate statistical significance (using the 2-sided 5% significance level), in the treatment comparison of tanezumab 20 mg + opioid versus placebo + opioid. Taking into account for the assessment of non-binding futility and efficacy at the interim analysis, the same sample size is expected to achieve 80 to 85% power.

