### 3. STUDY DESIGN

**Figure 1. Study Design**

This is a randomized, double-blind, placebo-controlled, multicenter, parallel-group Phase 3 study in cancer subjects requiring treatment with background opioids for pain due to bone metastasis.

The protocol was initially designed to include 3 treatment groups (tanezumab 20 mg SC, tanezumab 10 mg SC, and placebo), and was amended (Amendment 3) after study start to discontinue the tanezumab 10 mg dose arm. It is estimated that approximately 11 subjects in total were randomized to receive tanezumab 10 mg SC prior to implementation of Amendment 3.

Following implementation of Amendment 3, subjects were randomized in a 1:1 ratio (planned 85 subjects/arm) to one of two treatment arms: tanezumab 20 mg SC or matching placebo SC, each administered in addition to background opioids. Subjects who had been randomized to the 10 mg dose treatment arm and who were in the double-blind treatment period at the time of implementation of Amendment 3 were administered 20 mg for any remaining doses.

In protocol Amendment 4, the sample size has been reduced. A total of 155 subjects will be randomized. This comprises 144 subjects (72/treatment arm) randomized to receive tanezumab 20 mg SC or matching placebo SC plus an estimated 11 subjects previously randomized to receive tanezumab 10 mg SC.

Subjects will receive a total of 3 SC injections, separated by 8 weeks in addition to background opioids administered throughout the study. Treatment groups will include:

1. Placebo SC (matching tanezumab SC) in addition to background opioid therapy.

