#### **5.8.1.3. Restrictions on Use of Treatments for Underlying Cancer or Bone Metastasis**

Monoclonal antibodies used for the treatment of underlying cancer (eg, bevacizumab (Avastin), trastuzumab (Herceptin), panitumumab (Vectibix)) or bone metastasis (eg, denosumab (Prolia, Xgeva)) are generally permitted if ongoing at stable dose regimen at least 30 days prior to the first day of the Baseline Assessment Period (see [Section 5.8.2.3](#)). However, monoclonal antibody therapies associated with clinically significant peripheral or autonomic neuropathy or joint-related adverse effects or those based on chimeric or murine antibodies (eg, cetuximab (Erbix)) are prohibited within 90 days of the start of the Baseline Assessment Period and during the study until Week 32. Monoclonal antibody therapies which are not specifically listed as permitted (see [Appendix 8](#)) should be discussed with the study clinician on a case-by-case basis.

Small molecule inhibitors (eg, erlotinib (Tarceva), sunitinib (Sutent), lapatinib (Tykerb)) used in the treatment of underlying cancer or bone metastasis are permitted (except for bortezomib) if at a stable dose regimen at least 30 days prior to the first day of the Baseline Assessment Period.

If during the double-blind treatment period prior to Week 8, the subject's underlying cancer or bone metastasis progresses so as to require a new chemotherapy regimen, new concomitant bisphosphonates, new concomitant hormonal anti-cancer treatment, or initiation of radiotherapy to sites of bone metastasis, the subject should be withdrawn from study treatment (eg, due to disease progression) and entered in the Early Termination Follow-Up period (refer to [Section 6.4](#)). Between Week 8 to Week 32, if treatment for underlying cancer

or bone metastasis needs to be initiated or changed (refer to [Section 5.8.2.3](#)), the study clinician should be informed so that guidance may be provided as to whether the subject should be withdrawn from study treatment and entered in the Early Termination Follow-Up period. After the Week 32 visit, standard of care treatment may be prescribed as appropriate, without prior consultation with the study clinician.

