## **6.2.2. Double Blind Treatment Period**

### **6.2.2.1. Background Opioid Use**

After randomization and through Week 8, all subjects will continue to take the opioid regimen or morphine equivalent dose used during the Baseline Assessment Period. The average of the total daily opioid doses (ATC + IR) taken during the Baseline Assessment Period will be used as the Baseline total daily opioid dose.

Beginning on Day 1 and through Week 8, the average total daily dose of opioids between study clinic visits should not exceed the Baseline total daily morphine equivalent opioid dose by more than 10%. Subjects who require an opioid dose more than 10% greater than the Baseline total daily opioid dose should discontinue the Double-Blind Treatment Period for insufficient clinical response or disease progression ( per investigator's judgment) and enter the 6-month Safety Follow-Up period (refer to [Section 6.4](#)). Opioid dose reduction will be allowed if the subject experiences intolerable opioid side effects, if pain decreases or if the subject requests dose reduction. Once reduced, the opioid dose may be re-increased if needed for pain relief, but should not exceed the Baseline total daily morphine equivalent opioid dose by more than 10%.

Following the Week 8 clinic visit, subjects will remain on the opioid regimen used during the Baseline Assessment Period but will be allowed to change formulation, increase or decrease the amount of their background opioid medication without restriction if the investigator

considers such changes are necessary. Opioid reductions and increases will be done using accepted clinical guidelines (refer to [Section 6.1.1.2.4](#)).

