### 9.2.1. Primary Endpoint Analysis

The primary efficacy endpoint is the change from Baseline to Week 8 in the daily average pain intensity in the index bone metastasis cancer pain site measured by the 11-point Pain Intensity Numerical Rating Scale (NRS), where scores range from 0-10.

Baseline is defined as the mean average daily Pain NRS score during the Baseline Assessment Period prior to Randomization (expected to be 5 days). The Week 8 pain intensity value is the mean of the daily average Pain intensity scores for the 7 days prior to the Week 8 visit. If any of the seven Week 8 daily scores are missing then the Week 8 value will be calculated over the remaining observations.

The primary efficacy endpoint will be analyzed using an ANCOVA model, with model terms for Baseline score, the stratification variables, Baseline opioid use, region and treatment group. The stratification variables are (i) tumor aggressiveness (assessed by Eastern Cooperative Group [ECOG] performance status and (ii) presence/absence of concomitant anticancer treatment (eg, chemotherapy or hormonal therapy or anti-hormonal therapy).

The primary analysis of the primary endpoint will use multiple imputation for missing data, to account for uncertainty around the unobserved subject response. The basis for imputing missing values will be dependent on the reasons for missing data. For subjects with missing data due to discontinuation prior to Week 8 for lack of efficacy, or for an adverse event or death, imputation will be based on sampling from a normal distribution using a mean value equal to the subject's Baseline efficacy value and the standard deviation (over the placebo and tanezumab 20 mg treatment groups) of the observed efficacy data at Week 8. For subjects with missing data for any other reason, imputation will be based on sampling from a normal distribution using a mean value equal to subject's last observed efficacy value and standard deviation (over the placebo and tanezumab 20 mg treatment groups) of the observed efficacy data at Week 8. Imputed values will be truncated at 0 and 10, but not rounded. One hundred imputation samples will be used, and the ANCOVA model described above will be used for each imputation dataset. The final results will be calculated using the combined sets of results from each imputation dataset analysis.

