The significance level for the primary analysis of the primary endpoint at the interim and the final analysis will be determined in a way to have an overall two-sided 5% significance across analyses. The boundary to declare efficacy at the interim or the final analysis will be determined using the Lan-DeMets alpha spending function with the O'Brien-Fleming style boundary (refer to Section 9.6 for details). The non-binding futility stopping rule will not influence the efficacy boundary.

The primary efficacy population (Intent to Treat Set) is defined as all randomized subjects who received the Day 1 SC injection (either tanezumab SC or matching placebo SC). A

secondary efficacy population (Per-Protocol) is defined as all subjects in the Intent to Treat Set who were not major protocol deviators.

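### Do Section 9.1's 85% and 80 to 85% power figures overstate the power of the planned imputation analysis, because leavers are inside the 72 per arm?

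*Protocol*

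**What the plan says.** Section 9.1 plans on a targeted difference of -1.0 and a within-group SD of 2.0 taken from study A4091003, at the two-sided 5% level. It states that "a sample size of approximately 72 subjects per treatment group is required to achieve 85% power to demonstrate statistical significance", leaving the interim aside. Allowing for the futility and efficacy looks, "the same sample size is expected to achieve 80 to 85% power". The Protocol Summary repeats both statements.

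The 72 is also the number randomized. Section 3 says "This comprises 144 subjects (72/treatment arm) randomized to receive tanezumab 20 mg SC or matching placebo SC". Section 9.1 triggers the interim when "at least 50% (36 from each treatment group) of subjects have completed or discontinued prior to Week 8", so early leavers count towards it.

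The protocol provides for stopping before Week 8. Under Section 6.2.2.1, subjects who need clearly more opioid than at Baseline "should discontinue the Double-Blind Treatment Period for insufficient clinical response or disease progression". Under Section 5.8.1.3, if new cancer treatment is needed, "the subject should be withdrawn from study treatment (eg, due to disease progression" being the example given.

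Section 9.2.1 analyses "all randomized subjects who received the Day 1 SC injection". Missing Week 8 values are multiply imputed. "For subjects with missing data due to discontinuation prior to Week 8 for lack of efficacy, or for an adverse event or death", the draws centre on the subject's own Baseline. For other reasons they centre on the last observed score. No dropout rate appears anywhere, and Section 9.1 does not say whether -1.0 and 2.0 describe complete data or the imputed analysis.

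**The concern.** A plan normally either inflates the randomized number for dropout or says that its effect and SD already allow for it. This one does neither, and 72 serves as both the power number and the randomized number. Draws centred on Baseline pull a leaver's change towards zero, which dilutes the difference when losses are equal. The noise in the draws also adds variance. With the futility rule followed, the interim already brings power down to about 82%, so little margin remains above 80%. If the true power were well below the quoted range, a non-significant result would be more likely to be a false negative than the protocol suggests.

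**Working it through.** **Inputs.** Difference 1.0, SD 2.0 and 72 per arm come from Section 9.1. The interim look is at 36 to 45 per arm (Sections 9.1 and 9.6). Efficacy uses Lan-DeMets spending of O'Brien-Fleming type, and futility is non-binding at 10% conditional power under the current trend. The missing fraction f is an assumption throughout.

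**1. The fixed-sample figure.** n = 2 × (1.960 + 1.036)² × 2.0² / 1.0² = 71.8, so 72 per arm. The standard error is 2.0 × √(2/72) = 0.333, the drift is 1.0 / 0.333 = 3.0, and power = Φ(3.00 − 1.96) = 85.1%. The stated 85% reproduces.

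**2. With the interim.**

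| Look | Efficacy z, interim / final | Futility z | Power, futility followed | Power, futility ignored |
|---|---|---|---|---|
| 36 per arm (t = 0.50) | 2.963 / 1.969 | 0.751 | 81.8% | 85.0% |
| 45 per arm (t = 0.625) | 2.606 / 1.985 | 0.949 | 82.8% | 84.7% |

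The stated 80 to 85% reproduces.

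**3. If -1.0 and 2.0 are complete-data values.** With equal losses, all imputed around Baseline, and imputation noise left out, the drift becomes 3.0 × (1 − f). Ranges cover the two looks.

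| f | Futility followed | Futility ignored |
|---|---|---|
| 5% | 77.8–78.8% | 80.9–81.2% |
| 10% | 73.3–74.4% | 76.6–76.9% |
| 20% | 63.1–64.1% | 66.5–66.8% |

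Power crosses 80% at f of 2.3 to 3.6% (followed) or 6.1 to 6.4% (ignored).

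Simulating the Section 9.2.1 imputation adds the draw noise and the Baseline covariate. With the look at 40 per arm, Baseline-centred draws and futility followed, power is 77 to 81% at 5% missing and 68 to 75% at 10%. The ranges reflect weaker or stronger assumptions on how Baseline correlates with the change.

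**4. If -1.0 and 2.0 already describe the imputed analysis.** Steps 1 and 2 then stand as they are, because every dosed subject is analysed. An intermediate reading takes -1.0 as net of dropout but lets imputation variance come on top of 2.0:

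- With an assumed correlation of -0.3 between Baseline and change, simulated power is 85%, 82% and 80% at 5%, 10% and 20% missing (futility followed).
- With no gain from Baseline, it is 79–82%, 76–80% and 70–77%.

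**5. If losses differ between arms.** On the complete-data reading, with the simulation set as in step 3, 15% missing on placebo against 5% on tanezumab gives 83 to 86%. Baseline-centred draws then count against placebo. The reverse split gives 52 to 57%. The protocol gives no basis for choosing between them.

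**6. The SD.** Section 1.2.4.1.1 reports a 95% interval of -1.18 to 0.66 for A4091003, with 29 and 30 treated. The half-width is 0.92 and the standard error 0.92 / 2.002 = 0.459. The implied SD is 0.459 / √(1/29 + 1/30) = 1.76. At 1.76, 85% power without an interim needs 2 × 2.996² × 1.76² = 55.6, so 56 per arm. The dilution of step 3 then leaves 83.5 to 84.4% at 10% missing and 79.1 to 80.2% at 15%, with futility followed. That interval is for Week 6 after one intravenous 10 mg dose, so it is only a guide.

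**7. Withdrawal is not the same as missing data.** Section 6.4 and note d of Table 2 ask withdrawn subjects for weekly cancer pain scores until 16 weeks after the last dose. Early Termination Visit 1 falls about 8 weeks after the last dose, which is Week 8 for someone dosed once. Some leavers may therefore still supply a Week 8 score.

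**The case for a change.** The strongest case for a change is that the 72 plainly contains leavers, that the protocol itself requires some of them to stop treatment, and that a within-group SD from an earlier study would not normally include between-imputation variance. Even with -1.0 taken as net of dropout, power can slip below 80% at around 10% missing if Baseline explains little. Relabelling two statements and running a small simulation would be cheap, and readers may take 80% as a floor.

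Part of this stands. Section 9.1 does not state its missing-data basis, and on the complete-data reading with equal losses the shortfall is real and not small.

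It does not show that the stated power is wrong. Section 9.1 ties its 80 to 85% to the interim looks and does not offer it as a floor against every hazard. The one earlier effect reported for a comparable group, Baseline pain above 5, is on Baseline-carried-forward data (Section 1.2.4.1.1), so planning values that already allow for dropout are at least as plausible. Carrying Baseline forward adds no draw noise, which is a fair reservation, but the SD of 2.0 against an implied 1.76 leaves some room for it. A claim that power must be lower needs a dropout rate, an equal split and a completers-only reading of -1.0, and the protocol gives none of these.

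**Conclusion.** No change follows. Every figure in Section 9.1 reproduces: 85.1% without the interim, and about 82 to 85% with it. The gap is that the protocol does not say whether -1.0 and 2.0 come before or after missing-data handling. Depending on that answer and on the losses, power with the interim and futility followed could be about 68 to 75% (complete-data values, 10% missing in both arms) or stay at 82 to 86% (values net of imputation, or placebo losing 15% against 5%). All these cases rest on assumed dropout, and the simulated ones also on assumed Baseline correlations. None makes the stated power an error. Those who keep 72 per arm would only add a label or a sensitivity range. That leaves the sample size, the boundaries, the Section 9.2.1 analysis and the reading of the final estimate and its interval as they are. Anyone interpreting a non-significant result can weigh the observed missingness directly.

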## 9.2. Efficacy Analysis

Efficacy data from subjects randomized to the tanezumab 10 mg treatment group will be summarized but not included in analyses of efficacy.

### 9.2.1. Primary Endpoint Analysis

The primary efficacy endpoint is the change from Baseline to Week 8 in the daily average pain intensity in the index bone metastasis cancer pain site measured by the 11-point Pain Intensity Numerical Rating Scale (NRS), where scores range from 0-10.

Baseline is defined as the mean average daily Pain NRS score during the Baseline Assessment Period prior to Randomization (expected to be 5 days). The Week 8 pain intensity value is the mean of the daily average Pain intensity scores for the 7 days prior to the Week 8 visit. If any of the seven Week 8 daily scores are missing then the Week 8 value will be calculated over the remaining observations.

The primary efficacy endpoint will be analyzed using an ANCOVA model, with model terms for Baseline score, the stratification variables, Baseline opioid use, region and treatment group. The stratification variables are (i) tumor aggressiveness (assessed by Eastern Cooperative Group [ECOG] performance status and (ii) presence/absence of concomitant anticancer treatment (eg, chemotherapy or hormonal therapy or anti-hormonal therapy).

The primary analysis of the primary endpoint will use multiple imputation for missing data, to account for uncertainty around the unobserved subject response. The basis for imputing missing values will be dependent on the reasons for missing data. For subjects with missing data due to discontinuation prior to Week 8 for lack of efficacy, or for an adverse event or death, imputation will be based on sampling from a normal distribution using a mean value equal to the subject's Baseline efficacy value and the standard deviation (over the placebo and tanezumab 20 mg treatment groups) of the observed efficacy data at Week 8. For subjects with missing data for any other reason, imputation will be based on sampling from a normal distribution using a mean value equal to subject's last observed efficacy value and standard deviation (over the placebo and tanezumab 20 mg treatment groups) of the observed efficacy data at Week 8. Imputed values will be truncated at 0 and 10, but not rounded. One hundred imputation samples will be used, and the ANCOVA model described above will be used for each imputation dataset. The final results will be calculated using the combined sets of results from each imputation dataset analysis.

The significance level for the primary analysis of the primary endpoint at the interim and the final analysis will be determined in a way to have an overall two-sided 5% significance across analyses. The boundary to declare efficacy at the interim or the final analysis will be determined using the Lan-DeMets alpha spending function with the O'Brien-Fleming style boundary (refer to Section 9.6 for details). The non-binding futility stopping rule will not influence the efficacy boundary.

The primary efficacy population (Intent to Treat Set) is defined as all randomized subjects who received the Day 1 SC injection (either tanezumab SC or matching placebo SC). A

secondary efficacy population (Per-Protocol) is defined as all subjects in the Intent to Treat Set who were not major protocol deviators.

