#### **7.1.1.1. Index Bone Metastasis Cancer Pain Site Assessment**

At Screening, subjects will be asked to identify the most painful site of bone metastasis via IRT. This site will be considered the index bone metastasis cancer pain site. Subjects will be asked to record daily pain ratings for the index bone metastasis cancer pain site as described below.

Average pain and worst pain in the index bone metastasis cancer pain site will be assessed by the subject at Screening and daily during the Pre-Treatment Period to the Week 8 Visit, and then will be assessed weekly using a 24-hour recall period beginning after the Week 8 visit through Week 24 (and weekly during the Early Termination Follow-Up Period, as shown in [Table 2](#)). Refer to [Appendix 9](#) to see examples of the questions the subject will be asked.

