### 9.2.2. Secondary Efficacy Endpoint Analysis

Unless otherwise stated, all data up to Week 24 will be summarized, and data for the specified time points up to Week 24 will be analyzed.

The change from Baseline for the daily average and worst pain intensity in the bone metastasis index cancer pain site will be summarized for each week from 1 to 24. The change from Baseline to Weeks 1, 2, 4, 6, 8 (Worst Pain), 12, 16 and 24 will be analyzed using analysis of covariance (ANCOVA) as described above, using multiple imputation.

A secondary analysis for the change from Baseline in the daily average pain scores will use a repeated measures mixed effects model, on the available data over Weeks 1 to 24. Estimates for treatment groups and treatment difference for Weeks 1, 2, 4, 6, 8, 12, 16 and 24 will be shown. Additional secondary analysis for the change from Baseline to Week 8 and 16 in the daily average pain will use single imputation Last Observation Carried Forward (LOCF) and Baseline Observation Carried Forward (BOCF) for missing data.

The mean of the subject's average and worst pain in the non-index cancer sites, over all non-index sites (for up to 2 sites per subject) and for visceral non-index cancer sites will be calculated for Baseline and for each week, and for the change from Baseline. The change from Baseline to Weeks 1, 2, 4, 6, 8, 12, 16 and 24 in average and worst pain in the non-index cancer pain sites will be analyzed using analysis of covariance (ANCOVA) as described above, using multiple imputation. An additional analysis will utilize only those sites where Baseline average/worst pain is at least 5. If a subject has no nominated non-index sites (first analysis) or no nominated non-index sites where Baseline is at least 5 (second analysis) then that subject would be excluded from the respective analysis.

Additional ANCOVA analyses with multiple imputation for the primary endpoint will be used to examine the interaction of treatment group with study site, Baseline pain score, type of primary cancer (eg, breast, lung, etc), Baseline opioid use and the stratification parameters.

The change from Baseline to Weeks 2, 4, 8, 16, and 24 in the CCI [REDACTED] will also be summarized, and analyzed using the ANCOVA main effects model as described above with multiple imputation.

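### The imputation rule in Section 9.2.1 is tied to Week 8 and reused at Weeks 12, 16 and 24 without re-indexing, so the same reason for stopping is imputed differently before and after Week 8

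*Protocol*

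**What the plan says.** Section 9.2.1 sets out one multiple-imputation rule, for the change from Baseline to Week 8 in index-site average pain. It has two categories.

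- **Centred on Baseline:** "For subjects with missing data due to discontinuation prior to Week 8 for lack of efficacy, or for an adverse event or death".
- **Centred on the last observed value:** "For subjects with missing data for any other reason, imputation will be based on sampling from a normal distribution" with the subject's last observed efficacy value as its mean.

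Both categories take the SD, pooled over placebo and tanezumab 20 mg, "of the observed efficacy data at Week 8". Draws are truncated at 0 and 10.

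Section 9.2.2 then covers the other time points for index-site average and worst pain: "The change from Baseline to Weeks 1, 2, 4, 6, 8 (Worst Pain), 12, 16 and 24 will be analyzed using analysis of covariance (ANCOVA") in the way already described, with multiple imputation. The non-index sites get the same treatment at the same later weeks. The visible text contains no other multiple-imputation rule and no instruction to read the analysed week in place of Week 8.

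The measurement also changes at Week 8. Section 9.2.1 defines the Week 8 value as a mean over the seven days before the visit. Under Section 7.1.1.1, index-site pain "then will be assessed weekly using a 24-hour recall period beginning after the Week 8 visit through Week 24".

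**The concern.** The rule works at Week 8 because the cut-off and the analysed week coincide. At Week 24 they do not. A subject who dies in Week 14 did not discontinue before Week 8, so the first category does not apply and the remainder category does: the Week 24 value is drawn around the last, possibly improved, score. A subject who died in Week 7 has the Week 24 value drawn around Baseline. Nothing in the protocol gives a reason to treat the same event in two ways within one analysis.

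Such cases are foreseeable. Section 6.4 directs withdrawal for inadequate pain relief throughout the double-blind period, and the population has metastatic cancer. Section 1.2.5 gives maintenance of efficacy as one reason for the 24-week treatment period, so the later weeks will be read as evidence on that.

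The SD has the same indexing problem. A Week 8 seven-day mean supplies the spread for what are, after Week 8, single 24-hour ratings.

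**Working it through.** **1. The plan's own figure.** Section 9.1: SD 2.0, target difference -1.0, two-sided 5%, 85% power, 1:1 allocation.

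n per arm = 2 × (1.960 + 1.036)² × 2.0² / 1.0² = 71.8, rounded up to 72. Power at 72 per arm is 85.1% by the normal approximation. With the single interim look, power is 81.9% (interim at 36 per arm) to 82.9% (at 45 per arm) if the futility rule is obeyed, inside the stated 80 to 85%. None of this depends on the imputation at later weeks.

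**2. Applying the text at Week 24, value missing.**

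| Event | Before Week 8? | Category | Draw centred on |
|---|---|---|---|
| Death in Week 7 | Yes | First | Baseline |
| Death in Week 14 | No | Remainder | Last observed value |
| Lack-of-efficacy stop in Week 10, no later score | No | Remainder | Last observed value |

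At Weeks 1, 2, 4 and 6 the reason category does no harm, since any discontinuation before those weeks is also before Week 8. Only the SD is mismatched there.

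**3. Difference per affected subject.** Assumptions: Baseline 6 to 8, SD 2.0, draws limited to 0 to 10. Compared with Baseline centring, last-value centring gives a score lower by:

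- 0.89 to 0.98 points if the last improvement was 1 point
- 1.85 to 1.97 points if it was 2 points
- 2.84 to 2.93 points if it was 3 points

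So the gap is close to the last improvement itself, and truncation can be ignored below.

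**4. Effect on the between-arm difference.** Baseline centring imputes a mean change of about 0; last-value centring imputes a mean change equal to the last change. With p the proportion of an arm that stops for these reasons after Week 8 and has a missing value:

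shift ≈ p_T × (mean last change, tanezumab) − p_P × (mean last change, placebo)

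Negative values favour tanezumab. The protocol gives none of the four inputs; all rows are assumptions.

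| p_T | p_P | Last change T | Last change P | Shift |
|---|---|---|---|---|
| 10% | 20% | -1.5 | -1.0 | -0.15 + 0.20 = +0.05 |
| 20% | 20% | -1.5 | -1.5 | -0.30 + 0.30 = 0 |
| 10% | 10% | -1.5 | -0.5 | -0.15 + 0.05 = -0.10 |
| 15% | 15% | -2.0 | -1.0 | -0.30 + 0.15 = -0.15 |
| 20% | 15% | -2.0 | -1.0 | -0.40 + 0.15 = -0.25 |

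With equal proportions of 5%, 10% or 20% and last changes of -2 versus -1, the shift is -0.05, -0.10 or -0.20. The effect of the SD mismatch was not quantified.

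**The case against.** The best counter-argument is that nobody would program it this way. The Week 8 wording sits in a paragraph about the primary endpoint, so Week 8 may simply name that endpoint's time point, and the back-reference in Section 9.2.2 may attach to the ANCOVA alone. Section 9.2.2 also plans a mixed BOCF/LOCF rule for responder endpoints through Week 24, meant to mirror the primary imputation, which suggests that the reason-based principle was to carry forward. Section 9 leaves detail to a SAP that is not shown. As to intent, this is plausible. But the list of reasons in the responder paragraph is cut off in the public text, and no visible sentence makes the substitution. The protocol does not leave the rule open: it states one, with a fixed week.

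The commas in the first category allow another reading, in which only lack of efficacy is tied to Week 8. Lack-of-efficacy stops after Week 8 would still fall into the remainder.

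The second objection limits the size. Section 6.4 and Table 2 ask withdrawn subjects for weekly cancer pain scores until 16 weeks after the last dose. A subject who stops at Week 10 after the Week 8 dose is asked through Week 24 (8 + 16); after the Week 16 dose, through Week 32 (16 + 16). Section 9.2 does not say whether these scores enter the analysis. If they do, the affected group shrinks to deaths and subjects who stop reporting.

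Third, other analyses exist: a repeated-measures model over Weeks 1 to 24, and LOCF and BOCF for average pain at Weeks 8 and 16. The model applies no reason-based rule, and Weeks 12 and 24 have no BOCF.

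A reader might go further and infer that failures and deaths after Week 8 simply keep their improved score, so that the later results are biased towards tanezumab by up to a quarter of the target. The documents do not support that. Values are drawn around the last score, not fixed at it. Lack-of-efficacy stops plausibly have last scores near Baseline and would move little. The direction depends on unknown rates and can go against tanezumab.

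**Conclusion.** The point stands as a defect in the stated rule for the secondary analyses at Weeks 12, 16 and 24. As written, data missing after the same event are centred on Baseline or on the last observed value according to the side of Week 8 on which the event fell, and the SD is taken from a different week and a different kind of measurement.

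The primary endpoint, the significance level, the sample size and the power are untouched. The stated secondary objective is safety, so no formal objective rests on these analyses.

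The shift in the between-arm difference is about +0.05 to -0.25 NRS points over the assumed scenarios, and zero if the arms have equal proportions affected and equal last changes. The -0.25 is the most unfavourable scenario tried, not an estimate. These figures rest wholly on assumed proportions and last changes, and they count only values that are in fact missing after any post-withdrawal diary scores are used. The sponsor may have intended week-matched imputation; the text should say so.

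**What to change.** Add one sentence to Section 9.2.2, carried into the SAP: for each analysis week, Baseline-centred imputation applies to data missing because of discontinuation for lack of efficacy, adverse event or death before that week, and the imputation SD is that of the observed data at that same week.

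This needs no new data and leaves the Week 8 analysis as it is. The downside is that the Week 12 to 24 estimates may become somewhat less favourable.
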